Thermotape High-adhesion Medical Tape Comparison Study

June 21, 2022

Background:

Currently, modern medical tapes can be classified into two categories, high-adhesion tape, and low-adhesion tape. Both tapes, however, are not sufficient for use in a medical environment; high-adhesion tape, when removed, can cause medical adhesive related skin injuries (MARSI), which is liable to cause patients to have to return to the hospital to treat it, resulting in a dramatic increase in medical expenses once fully recovered. Conversely, low-adhesion tape is ill-suited for securing medical devices, such as IV lines, in place because of having low adhesion. As a result, a patient's ability to recover is impacted, overall increase medical expenses from an extended stay at the hospital.

Thermotape is designed to combat both flaws, by acting as a high-adhesion tape until heated, where it can be removed as easily as low-adhesion tape.

Objective:

This objective of this study is to compare the safety and performance of Thermotape compared to Tegaderm™ tape and Kind™ tape over the course of 24 hours. In regard to safety, pain inflicted during removal and any potential effects will be monitored for Thermotape versus Tegaderm™ and Kind™ tape.

Design:

A single blinded comparative clinical study, where researchers will know the tape being applied while the subjects do not.

Methods:

Consent will be obtained from the subject as they enter the building for tape application. This will be done by providing a paper consent form detailing the necessary details concerning the trial. If consent is obtained, they will be allowed into the room for tape application.

Before tape application, both forearms will be cleaned using an isopropyl alcohol wipe and skin markers will be used to draw lines, with two inches of spacing between, to separate areas of tape application. The marks began at the elbow and continued down the forearm. Following the pre-tape preparations process, Thermotape, Kind™ tape, and Tegaderm™ tape will be applied horizontally, in vertical

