succession. Following Thermotape's application, a finger will be used to rub Thermotape in a vertical motion to ensure that the tape, especially edges, are fully adhered. The same procedure will be used for Kind™, however Tegaderm™ will not require the same adhesion procedure, as noted by a nurse practitioner. The tapes will be applied in a random order. Once all tapes are applied, researchers will give the following speech: "Now that the tapes have been applied, please do not do any physically extraneous activities, like swimming in the ocean, running a marathon, or storm chasing. Basically, any activities that make you sweat. Additionally, please do not shower until we remove the tapes, even if you really want to. If you do end up getting the tapes wet, through sweat or by showering, please note it down in the activity log on the back of your activity log. Also, try not to pick at the tapes, even if the corners start lifting. Thank you and we'll see you back tomorrow!" The speech requests that subjects are to not participate in strenuous physical activity or shower for the duration of the 24-hour study. One researcher is to apply the tape to the participants. Each tape will be cut 1 inch wide by 2 inches long.

When subjects return for tape removal, they will be given a pain survey, with a 0-to-10 Wong-Baker scale, to fill out after each piece of tape is removed. One photo will also be taken of the forearms to document the state of the subject's forearms 15 minutes after tape removal. Each piece of tape is then to be analyzed for wear using a 0-to-7 point scale.

When removing the tapes, an edge will first be lifted and then it will be peeled at an angle of 180° at a consistent rate. If a hair is encountered, the tape will be removed following the root of the hair to its tip. After the removal of each piece of tape, it will be placed on a glass slide and taped down for later quantification of cell and hair counting caused by tape removal. No gloves will be used throughout the process. During removal, if a subject shows signs of extreme discomfort or the skin appears to start tearing, manual removal will be stopped and a commercial silicon-based remover, Brava, will be used to remove the tape instead. To do so, Brava will be rubbed all over the tape, including the edges, and under the skin after removal of the tape. Gloves will be used in the case of using Brava to remove tape.

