Removal of tape from both forearms will stay consistent, however one forearm (left), will use a Dynarex heat pack to assist in tape removal. Prior to heat pack activation, a corner for each tape sample will be lifted. After, the heat pack will be activated and kneaded for one minute before application onto the subject's skin. Then, the heat pack will be folded in half and applied to each piece of tape for 30 seconds before removal. The heat pack will be kneaded for 20 seconds between each tape removal.

Following the removal of all pieces of tape, the pain survey is collected, and each subject will be asked to wait 15 minutes following removal to examine for any redness that may have occurred. A 0-to-4 point scale will then be used to assess for erythema present on the forearms.

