## Primary Results:

### Pain experienced from Removal

The following 0-to-10-point Wong Baker scale will be used to quantify pain experienced by the subject during tape removal:

Subjects are to use the scale to determine the level of pain experienced after each piece of tape is removed and researchers are to record the number determined. Whole numbers between each face may be used as well.

The average for each population group will be obtained after data has been collected from the participants.

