### Skin Irritation

The following 0-to-4-point scale will be used to quantify the redness of the skin after tape removal:

Grade	Erythema/Irritation
0	None - natural skin tone
1	Slight - Barely visible increase in pink coloration
2	Mild - Visible increase in light pink coloration
3	Moderate - Diffuse pink coloration, localized or diffuse areas of reddened skin
4	Severe - Intense redness, diffused or localized

The average for each population group will be obtained after data has been collected from participants.

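### How tape positions are randomised, for which unit and with what balance is not specified, so any position effect may add avoidable variance to tape contrasts and some heat contrasts

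*Protocol*

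**What the plan says.** All of the design text is in the Protocol, Methods. Both arms are used: "both forearms will be cleaned using an isopropyl alcohol wipe". The skin is marked to separate the tape areas, and "The marks began at the elbow and continued down the forearm". One strip each of Thermotape, Kind and Tegaderm is then placed, one below another. The only rule linking tape to place is "The tapes will be applied in a random order".

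Heat is assigned by side: "one forearm (left), will use a Dynarex heat pack to assist in tape removal". The order in which strips are removed is not stated.

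In the SAP, the plan for pain (Pain experienced from Removal) is "The average for each population group will be obtained after data has been collected from the participants", and Skin Irritation has almost the same sentence. Skin Cells, Tape Wear and Hair Follicles also call for averages. No visible section uses position or subject.

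The available text of the SAP lacks one figure and one passage. Either could show the layout or the sample size, so the statements here are limited to the visible text.

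**The concern.** One strip lies nearest a bending joint and the others lie further down the arm. Pain, redness, hair, cells and wear could plausibly depend on that level, although the documents do not say that they do. Heating gives a second route. One activated pack is applied to the strips in turn, so if removal follows position, the level on the arm also sets how long after activation each strip is heated.

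Three tapes in three places give only six possible orders, which is few enough to use each equally often. If the order is instead an unrestricted draw, one tape can by chance sit at the elbow more often than another. Plain averages would carry that imbalance into the tape comparison. If each arm has its own draw, a tape is at the same level on both arms in only one subject in three. Comparing that tape heated and unheated then also compares two levels. Thermotape is designed to release when heated, so this single-tape comparison matters.

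**Working it through.** The plan has no figure to reproduce: the visible text gives no sample size, SD, effect size, alpha or power.

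**Inputs from the documents:** three tapes per arm, hence 3! = 6 orders; two arms; heat on the left; plain averages.

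**Assumptions:** orders drawn without restriction; an additive position effect in which the elbow site differs from the other two by d points; an SD of 2 for the paired difference on the 0-10 pain scale, excluding position; d = 0.5, 1 or 2.

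**Position variance per subject**

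- *Tape contrast within one arm.* The difference is +d, −d or 0, each with probability 1/3. Mean 0, variance (2/3)d².
- *One tape, heated minus unheated, arms drawn separately.* Each arm contributes (1/3)(2/3)d² = (2/9)d², so the total is (4/9)d². With a shared order it is 0.
- *Tape-by-heat contrast, arms drawn separately.* (2/3)d² + (2/3)d² = (4/3)d². With a shared order it is 0.
- *Heat contrast averaged over three tapes.* 0 in every case, because each arm holds all three positions.
- *Tape contrast averaged over both arms.* (1/4)(2/3 + 2/3)d² = (1/3)d² if the arms are drawn separately, and (2/3)d² if they share an order without balance over subjects.

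**Widening of the standard error** (ratio to the same contrast without position variance)

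| d (points) | Tape, one arm: √((4 + 0.667d²)/4) | One tape's heat contrast, separate draws: √((4 + 0.444d²)/4) |
|---|---|---|
| 0.5 | √(4.167/4) = 1.02 | √(4.111/4) = 1.01 |
| 1 | √(4.667/4) = 1.08 | √(4.444/4) = 1.05 |
| 2 | √(6.667/4) = 1.29 | √(5.778/4) = 1.20 |

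These ratios do not depend on n. For an assumed n of 20, the chance error in the mean one-arm tape contrast has SD d√(2/(3 × 20)) = 0.18d.

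**Check with another shape of effect.** Suppose the effect is linear, with d points per step from elbow to wrist. The variances become 2d² (tape, one arm) and (4/3)d² (one tape's heat contrast, separate draws). At SD 2 the tape standard error widens by √(4.5/4) = 1.06 for d = 0.5 and √(6/4) = 1.22 for d = 1. With an assumed n of 20, true difference of 1 and two-sided alpha of 0.05, power for the one-arm tape contrast is 61% without position variance, 56% at d = 0.5 and 45% at d = 1.

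**After the change.** With the six orders used equally often, position contributes 0 to the mean tape contrasts. With a shared order it contributes 0 to each tape's heat contrast. Both results assume additive effects, and the second also assumes the same position effect on both arms.

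**The case against.** The strongest reply is that random allocation within a subject is a legitimate design. It gives zero expected bias in the tape contrast, chance imbalance is ordinary sampling error, and restricting the randomisation is a gain in efficiency. This stands. A position term in a within-subject model would also recover most of the loss, even after an unrestricted draw.

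Three stronger readings are tempting, and the documents support none of them.

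- *That the draw is simple, unbalanced and different on each arm.* The text says only that order is random. The supportable statement is that method, unit and balance are not specified. The remark "Removal of tape from both forearms will stay consistent" does not settle it either way, because it concerns how tape is removed and not where each tape lies.
- *That position biases the tape comparison.* It does not in expectation, if random order means random position. The word could instead mean the time sequence of application. Position would then not be stated to be randomised at all, which is a further reason to specify it.
- *That position contaminates the heat comparison generally.* It enters only single-tape and tape-by-heat contrasts, and only with separate draws.

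The sizes also rest wholly on assumptions. At d = 0.5 the loss is about 1% to 2%. A d of 2 is conceivable on the 0-10 pain scale, but would be half the range of the 0-4 erythema scale. Finally, the visible SAP names no standard error, test or model, so a position term presupposes an analysis still to be written. That limits the weight of the point but does not remove the gap.

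**Conclusion.** The point holds as a gap in specification with an efficiency cost. Neither the stated allocation rule nor the visible analysis controls position, and a reader cannot tell whether positions are balanced.

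Under an unrestricted draw, an elbow-only effect of 0.5 to 2 points and a paired-difference SD of 2 on the pain scale, the one-arm tape standard error is about 2% to 29% too wide. With separate draws for the two arms, a single-tape heat contrast is about 1% to 20% too wide. If there is no position effect, or if balance is already planned in text not visible here, the cost is nil.

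The change is worth making because it costs little, not because a large loss has been shown. It does not touch the fact that heat is always on the left arm, which ties heat to side and needs its own answer.

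**What to change.** Replace the sentence on order in the Protocol, Methods with:

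> *A computer-generated list assigns the six possible elbow-to-wrist tape orders equally often in blocks of six subjects; the same order is used on both forearms of a subject.*

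Use both parts together. A shared order without balance doubles the position variance of the two-arm tape average, from (1/3)d² to (2/3)d².

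Record position (1 to 3) for each strip, and the order of removal. In the SAP, include subject and position when estimating the tape and heat differences. Balance removes position from the averages. The position term removes it from the standard errors and deals with an incomplete final block.

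The cost is a pre-printed list, one recorded field for position (a second if removal order is noted) and one model term for position, with no extra subjects or visits.

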### Tape Wear

The following 0-to-7-point scale will be used to examine the wear of the tape when subjects come in for tape removal:

Grade	Wear/Adhesion Description
0	Test strip off
1	Test strip almost off
2	$\frac{3}{4}$ of test strip off
3	$\frac{1}{2}$ of test strip off
4	$\frac{1}{4}$ of test strip off
5	3 to 4 edges lifted
6	1 to 2 edges lifted
7	All corners adhered

An average will be taken for the tapes to determine how much wear is experienced for tape brand. An activity log will also be collected from each participant to determine the probable cause of tape wear if a grade three or below are obtained.

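### The scripted instructions and the SAP give skin symptoms during the 24 hours of wear no route into the data, and a strip taken off because of a reaction would enter the wear average as a zero

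*Protocol*

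**What the plan says.** - **Safety objective.** The Protocol's Objective compares safety and performance "over the course of 24 hours" and states that "pain inflicted during removal and any potential effects will be monitored".
- **Instructions to subjects.** The speech in the Protocol's Methods section is given word for word. Its only logging request is "If you do end up getting the tapes wet, through sweat or by showering, please note it down in the activity log". It also tells subjects to "try not to pick at the tapes, even if the corners start lifting".
- **Skin assessment.** In Methods, "each subject will be asked to wait 15 minutes following removal to examine for any redness that may have occurred"; one photo of the forearms is taken at the same time. In the SAP, Skin Irritation, a "0-to-4-point scale will be used to quantify the redness of the skin after tape removal".
- **Trigger for changing the removal method.** It is confined to removal: "During removal, if a subject shows signs of extreme discomfort or the skin appears to start tearing, manual removal will be stopped".
- **Wear.** In the SAP, Tape Wear, a strip that has come off gets grade 0, the lowest of a scale running to 7, and grades are averaged by brand. The activity log is collected to "determine the probable cause of tape wear if a grade three or below are obtained".
- **Water loss.** The SAP's TEWL section measures taped and untaped skin but gives no time of measurement.

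**The concern.** A tape can harm skin while it is worn as well as when it is pulled off, and the Objective is wide enough to cover both. If wear-period complaints are not requested, a reaction can be missed in two ways. It may leave no redness at the visit. Or it may lead the subject to take the strip off, in which case the site arrives bare and is graded on a wear scale.

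The second way matters more for a comparison of tapes. The tape that irritates most during wear would lose wear score and might gain nothing in the safety results, so a safety signal could be read as a performance result.

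**Working it through.** The plan gives no figure to reproduce: the supplied text has no sample size, expected event rate or rule for lost strips. The check is therefore a reading of what is collected and when, followed by one piece of arithmetic.

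**Step 1. What each measure can see of a reaction during wear.**

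| Measure | When | What it captures of a wear-period reaction |
|---|---|---|
| Activity log, as scripted | During wear | Wetting only; no symptom, and no reason for early loss, is requested |
| Pain score (Wong-Baker) | After each strip is removed | Removal pain |
| Trigger for changing the removal method | During removal | Discomfort or tearing at removal |
| Erythema grade 0 to 4 and photo | 15 minutes after removal | Redness still present; no item for itching or burning |
| TEWL | Not stated | Water loss, not symptoms |

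No row asks the subject about symptoms during wear or on return.

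**Step 2. What the erythema grade can attribute.** Redness at 15 minutes can come from wear, from peeling or, on the left arm, from the heat pack. The supplied text has no grade taken before removal, so these sources cannot be separated for a given site. A persistent rash is therefore recorded, but its cause is not.

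**Step 3. What happens to a strip taken off early because of a reaction.**
1. The strip is off on return, so the scale gives grade 0.
2. Grade 0 is at or below 3, so the log is consulted for a cause.
3. The script did not ask the subject to write that cause down.
4. If a cause is found anyway, no rule changes the grade, excludes it from the mean or counts it as a skin event.
5. The 0 enters the brand average.

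**Step 4. Size of the effect on mean wear.** Let n be the number of strips in a brand's average and g the grade the strip would otherwise have had. Replacing g by 0 lowers the mean by g/n. The largest possible g is 7, so the upper limit is 7/n. Since n is not given, a range is shown, with all other strips assumed to be at grade 7:

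| n (assumed) | Mean with one 0 | Fall, 7/n |
|---|---|---|
| 10 | 63/10 = 6.30 | 0.70 |
| 20 | 133/20 = 6.65 | 0.35 |
| 30 | 203/30 = 6.77 | 0.23 |
| 50 | 343/50 = 6.86 | 0.14 |

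These are falls per affected strip. How many strips would be affected cannot be derived from the documents.

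**The case against.** The strongest reply is that silence in the speech does not prove that nothing is collected. The speech places the wetting note on the back of the log, so the form has a front whose fields are not shown. The consent form and part of the SAP are also not available here, and either might carry a reporting instruction. This stands. The gap is established for the script and the supplied text, and a reader should not infer that the log itself holds nothing but wetting.

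Second, a reader might infer that rash goes uncollected. The documents do not support that. Erythema on the forearms is graded and photographed, nothing excludes a site whose strip came off early, and the skin-marker lines separate the sites. Redness that lasts to the visit would count in a primary result. What remains is that its cause cannot be separated, and that symptoms without redness and faded reactions are lost.

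Third, a reader might infer that the plan classes a deliberate removal as adhesive failure. It does not say so. Grade 0 describes the state of the strip, and the log look-up appears meant to sort out causes. But that look-up relies on information subjects are not asked to give, and nothing follows from its result.

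Fourth, subjects are told not to pick at the tapes, so early removal may be rare. This is fair, and no rate is claimed. It does not touch the loss of symptoms under strips that stay on.

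Finally, the one safety effect that the Objective names is removal pain, and the primary results address it directly. It would therefore be too strong to say that the study cannot support its safety objective. The weakness lies in the part that reaches beyond removal pain to other effects.

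**Conclusion.** The point holds as a gap in collection and handling. The safety objective spans the wear period, yet the scripted request covers wetting alone and no supplied section asks about skin symptoms during wear or on return. Symptoms without redness and reactions that fade before the visit leave no record. Redness that persists is recorded but cannot be attributed to wear.

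A strip taken off for a reaction would, by following the scale as written, be averaged as a 0. That is an inference from the scale and from the absence of any rule, not a stated instruction. The direction is clear: the mean wear of the irritating tape falls. The size per strip is at most 7/n, and reaches that limit only if the strip would otherwise have scored 7; both n and the frequency of such removals are unknown.

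The conclusion rests on the log form and the unseen consent and SAP material containing no symptom or reason-for-loss request. If they do contain one, the collection part falls away, and what remains is the missing SAP rule for using the answers. The change should be made before data collection, because complaints not asked for at the time cannot be reliably recovered later.

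**What to change.** **Script and log.** First check whether the log form already has these fields. If not, add, by marked position: any itching, burning, pain or rash under a strip, with its time; and any strip removed or fallen off, with time and reason. Recording by position keeps subjects blinded; a key linking position to tape is needed because the order is random.

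**Return visit.** Before removal starts, ask the same question for each position. Use fixed wording, since the researchers know which tape is which.

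**SAP.** Report the number of sites with a wear-period skin complaint per tape. List strips removed because of a skin complaint as skin events. Show mean wear with and without those strips.

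**Cost.** One revised log page, an addition to the script, one question at a visit already planned and one extra table; no extra staff or visits. The downside is some additional minor reports. These may not be fully equal across tapes: Thermotape and Kind are rubbed down after application and Tegaderm is not, which subjects can see, so blinding does not guarantee even reporting.

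### Does the plan leave tape wear to be graded only after staff have lifted or removed the strips?

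*Protocol*

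**What the plan says.** The Protocol's Methods section introduces the return visit with "When subjects return for tape removal, they will be given a pain survey". It then mentions a photograph of the subject's "forearms 15 minutes after tape removal", and closes the paragraph with "Each piece of tape is then to be analyzed for wear using a 0-to-7 point scale".

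The next paragraph gives the removal technique, in which "an edge will first be lifted and then it will be peeled". The heat-pack paragraph follows and adds a step for the left forearm: "Prior to heat pack activation, a corner for each tape sample will be lifted". The pack is then activated and kneaded for one minute, held on each strip for 30 seconds, and kneaded for 20 seconds between strips.

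The SAP, under Tape Wear, states that the 0-to-7 scale "will be used to examine the wear of the tape when subjects come in for tape removal". Grade 0 is a strip that has come off, grades 1 to 4 describe how much is detached, grades 5 and 6 count lifted edges, and grade 7 is "All corners adhered". For the analysis, "An average will be taken for the tapes to determine how much wear is experienced for tape brand". The activity log is consulted for the likely cause when the grade is three or lower. Tape wear is listed under the secondary results.

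**The concern.** Two readings could spoil the grades. In the first, *then* in the Protocol is taken as a time order. Wear would be graded after the photograph, when every strip is already off the skin and on a slide. Applied literally, the scale would give every strip grade 0.

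In the second, wear is graded at the visit but strip by strip, just before each removal. On the left forearm a corner of every strip would by then have been lifted by staff. A strip that stayed fully attached for 24 hours could not score 7 there. The SAP states no split by forearm, so these grades would be pooled with those from the right arm.

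Tape wear is the only one of the six results in the SAP that grades adhesion, and adhesion until heating is what Thermotape claims to offer. A grade that recorded staff handling instead of wear would weaken that part of the comparison. The primary results, pain and irritation, are not touched.

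**Working it through.** The plan gives no figure to reproduce, so the check is a reading of the texts against the scale, followed by a look at how far the second reading could reach.

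**What each time of grading would mean for the scale**

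| Time of grading | Grades available | Support in the documents |
|---|---|---|
| On arrival, before any lift | 0 to 7 | SAP, Tape Wear; scale anchors; use of the activity log |
| After a staff lift, before removal | at best 6 if the staff lift is scored | none |
| After removal | 0 for every strip, read literally | only the word *then* in the Protocol |

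**Is the Protocol paragraph in time order?** No. It opens with the subject's return, goes to a survey filled in after each removal, then to a photograph taken 15 minutes after removal, then to wear. Removal itself is described only in the next paragraph. The paragraph lists what is collected at the visit. Its *then* is therefore weak evidence of sequence.

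**Where are the staff lifts described?** Both come after the wear sentence: the edge lift in the next paragraph and the left-arm corner lift in the one after that. Document order therefore does not place a lift before grading.

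**What is wear meant to measure?** The SAP looks to the subject's activity log to explain grades of three or lower. That makes wear a record of the 24 hours at home, not of handling at the visit.

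**Reach of the second reading**

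- Strips per subject: 3 tapes × 2 forearms = 6. Left-arm strips with a staff-lifted corner: 3 of 6.
- Shortest time from corner lift to end of heating, leaving out peel time: 60 + 30 = 90 s for the first strip, 90 + 20 + 30 = 140 s for the second, 140 + 20 + 30 = 190 s for the third. There is time in which a strip could be graded late.
- Suppose a staff lift were scored as wear, freed at most the two edges that meet at the corner, and detached less than a quarter of the strip. A left-arm strip would then move by 0 or −1 grade. Pooled with one unaffected right-arm strip, the tape's mean would move by between 0 and (−1 + 0)/2 = −0.5.

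The last step is a conditional ceiling, not an estimate. The SAP defines grade 7 by corners and grades 5 and 6 by edges, and gives no rule for turning a lifted corner into a number of edges. Any figure between 0 and 0.5 also needs the share of strips truly at grade 7, and the documents contain no wear data.

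**The case for a change.** The case for amending is that the texts do not settle the order. Elsewhere the Protocol uses *then* for real sequence, as in "an edge will first be lifted and then it will be peeled", so a literal reader could grade after removal. The SAP phrase may mean only that grading happens at the removal visit. A grader who knows that the tape must be on the skin could still grade each strip just before peeling it, which on the left arm is after the corner lift. Lost top grades would fall hardest on the tape that adheres best, averaging by brand would hide the loss, and one sentence in each document would rule it out.

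Part of this stands. The wording does differ, and no visible sentence says that grading precedes the lift. (A figure in the SAP and one further part of it were not available to read, so absence can be claimed only for the visible text.)

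The rest does not carry. Late grading does harm only if three things happen together: grading is done strip by strip instead of on arrival, it falls between the lift and the removal on the heated arm, and the grader scores a lift that staff have just made as 24-hour wear. No section describes any of the three. The corner lift is also made on all three tapes, and the text shows no direction of bias between them. The visible SAP plans an average for wear, with no test or threshold for a difference to cross.

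**Conclusion.** This is a minor wording inconsistency about a secondary result, and no change to the plan follows. The SAP states the time of grading, and its natural sense is on arrival with the strips still in place. The scale works in full only at that point, and the Protocol's order of description does not contradict it once its return-visit paragraph is read as a list. A sentence fixing the order would write down what sensible staff would already do.

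Under that reading the effect on the wear averages is zero. The late-grading scenario would involve 3 of 6 strips per subject. Its ceiling of half a grade in a tape's mean rests on a corner-to-edge rule that the SAP does not contain and on grader behaviour that neither document describes, so it should not be quoted as a likely error.

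The conclusion assumes that staff grade a strip as the subject brings it in and that the unavailable parts of the SAP do not order grading differently. Records showing that wear was graded after the corner lift would reopen the question for the left-arm grades only.

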## **Secondary Results:**

### Skin Cells

To prepare cells for examination, the cells on the tape will be transferred to a glass slide and heat fixed. After, one drop of methylene blue will be added to the center of the slide and a glass slide cover will be gently placed on the dye. A paper towel is then used to diffuse the excessive dye out of the slide cover. An optical microscope will then be used to examine for skin cells at 10x magnification.

Five images will be taken from each tape and an algorithm will be used to count the number of cells within the image. An average will be taken for each population group.

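### Strips for the secondary skin-cell count are peeled and mounted ungloved, and no stated rule keeps finger-touched adhesive out of the counted images

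*Protocol*

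**What the plan says.** In the Protocol's Methods, removal runs as follows: "When removing the tapes, an edge will first be lifted and then it will be peeled at an angle of 180° at a consistent rate". After the peel, each strip is handled again: "it will be placed on a glass slide and taped down for later quantification of cell and hair counting caused by tape removal". The next sentence is "No gloves will be used throughout the process". The one exception comes at the end of the same paragraph: "Gloves will be used in the case of using Brava to remove tape". On the left arm, the heat-pack paragraph adds "Prior to heat pack activation, a corner for each tape sample will be lifted".

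The SAP, under Skin Cells, begins from the point where "the cells on the tape will be transferred to a glass slide and heat fixed". A single drop of stain then goes in the middle of the slide and is covered. The count follows: "Five images will be taken from each tape and an algorithm will be used to count the number of cells within the image". Counts are averaged by group.

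The available text names no forceps or tab, no part of the strip reserved for holding, no rule on image position, no background count, and no means of telling staff cells from subject cells. One part of the SAP and one figure are not in the available text, so a control described there cannot be ruled out.

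**The concern.** The count is meant to measure skin taken off the subject by each tape. Adhesive collects skin cells, which is why the strip can serve as the specimen, and it can collect them from a researcher's fingertip as well. The staining and counting steps described do not identify whose cells are in the image.

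At stake is the meaning of the skin-cell average for each group. A background from handling would be added to it and could not be separated out once the slides are made, so it has to be prevented at collection.

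**Working it through.** The plan attaches no figure to this point, so there is nothing to reproduce. The check is a reading of the text plus three illustrations, whose assumptions are marked.

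**1. Does the no-glove rule reach the specimen?** Yes. The sentence follows the lift, peel and mounting steps and speaks of the whole process. That fingers touch the adhesive is an inference: no gloves are worn, no instrument is named, and an edge or corner must be lifted.

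**2. Overlap under random image placement.**
- Strip size, from Methods: "Each tape will be cut 1 inch wide by 2 inches long". Area = 2.54 × 5.08 = 12.90 cm².
- Assumed touched area a = 0.5, 1 or 2 cm². Touched share f = a / 12.90 = 3.9%, 7.8% or 15.5%.
- Chance that at least one of five independent, randomly placed images falls there = 1 − (1 − f)⁵ = 17.9%, 33.2% or 56.9%.

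**3. Overlap given the stain position.** The SAP stains the centre of the slide, while the contact points the Protocol names are an edge and a corner. Suppose the touched area is a band across the 2.54 cm width at one end.
- Depth of the band = a / 2.54 = 0.20, 0.39 or 0.79 cm.
- The midpoint of the strip lies 5.08 / 2 = 2.54 cm from that end, so even the deepest band stops 2.54 − 0.79 = 1.75 cm short of it.

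If the transfer preserves position and the cover is small, overlap would be well below the figures in step 2. The documents do not give the cover size, the transfer method, the image positions, or the contact points during mounting, so overlap is not excluded.

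**4. What a background would do to a comparison.** Let R be the true ratio of cells removed (higher-count tape to lower-count tape). Let c_hi and c_lo be the background on each, relative to the lower tape's true count. The observed ratio is (R + c_hi) / (1 + c_lo). With R = 2.0 assumed:

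| c_lo | c_hi | Observed ratio |
|---|---|---|
| 0.1 | 0.1 | 2.1 / 1.1 = 1.91 |
| 0.5 | 0.5 | 2.5 / 1.5 = 1.67 |
| 0.1 | 0.3 | 2.3 / 1.1 = 2.09 |
| 0.1 | 0.5 | 2.5 / 1.1 = 2.27 |

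The ratio is unbiased only when c_hi = R × c_lo. On the difference scale the shift is c_hi − c_lo, so an equal background cancels. An equal background therefore dilutes a ratio and leaves a difference alone, while an unequal one can move either in either direction. The documents give no value for R, c_hi or c_lo.

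**The case against.** The strongest reply is that this is a bench detail on one secondary endpoint, with no demonstrated effect. Much of that stands. The count covers five images after a transfer step, not the whole strip, and the stain goes in the middle, away from the edge or corner that is lifted. A chance of overlap is also not a shift in cell count, since the cell yield per touch is unknown.

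A reader might go further and infer that the background must differ between tapes or arms and so biases those contrasts. The documents do not support that, for three reasons:

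- **Tack.** It is plausible that a stickier adhesive takes more from a finger. Nothing in the text shows it for strips already worn for 24 hours.
- **Arm.** The left-arm corner lift could be an additional touch. It could equally be the lift that every strip receives, done earlier; the Protocol also says removal is to stay consistent across forearms.
- **Brava.** These strips are gloved, so their handling does differ. But the remover is also rubbed over the whole strip, a larger difference than the gloves.

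Nor should the no-glove sentence be stretched to cutting the tape, because it sits in the removal paragraph.

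What the reply does not remove is the gap itself: ungloved handling of the specimen is specified, and no visible rule keeps the handled part out of the count.

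**Conclusion.** The point holds as a limited one. Staff cells could enter the secondary skin-cell count, and nothing in the available text prevents or measures it. The size and direction of any bias, and whether it varies by tape or arm, cannot be determined from the documents.

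The 18%, 33% and 57% figures are an upper illustration. They rest on assumed touched areas and on random image placement, which the central stain makes unlikely. The conclusion also assumes that fingers meet the adhesive at the lifted end and that the unavailable part of the SAP contains no handling control. Pain and erythema do not depend on the count and are unaffected.

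**What to change.** Add a specimen-handling rule for every strip on both arms:

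1. Mark one end of the strip, and lift and grip it only there.
2. Mount it by that same end, using gloves or forceps only once the peel is complete. The peel stays as written, so the change does not touch the conditions behind the primary pain score.
3. In the SAP, exclude the marked end from the cell transfer and from the five images.
4. Record which strips were removed with Brava and report their cell counts separately.

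An unworn strip of each brand put through the same handling could be shown as description. It should not be used as a correction: one blank per brand is a single observation, its adhesive is fresh rather than worn, and it says nothing about the heated-versus-unheated contrast.

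The cost is one extra marking step, a sentence or two in each document, and a slightly smaller countable area. Excluding an end band equal to the touched areas assumed above would give up 3.9% to 15.5% of the strip.
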